9.2.3 Patient care endpoints

9.2.3.1 Investigator questionnaires

Site investigators (one per site) will be asked to complete the Overall Study Experience-sites (OSES) questionnaire. The OSES has 2 parts:

- OSES part 1 contains 1 item to examine resource requirements: “Approximately how much time did you spend with this participant (in person or via phone) during this scheduled visit/communication?”. OSES part 1 will be administered following each study visit.
- OSES part 2 contains 2 items to examine relationship (“I had a good relationship with this patient during the study”) and satisfaction with care (“I am satisfied with the level of care I have provided for this participant in this study”). OSES part 2 will be administered at Week 24 (Visit 12) only.

Each item is scored separately.

See questionnaire in [Appendix D](#).

9.2.3.2 Patient interviews

English-speaking patients of the virtual group who consent will be invited to participate in interviews following their Week 24 (Visit 12) study visit (ie, after completion of the trial). These qualitative exit interviews will be conducted one-on-one with up to 30 patients to:

- Examine patients’ experiences of trial participation, in their own words
- Explore the positive and negative aspects of trial participation
- Provide some context to responses given in the PRO questionnaires

Interviews will be held by trained site staff.

See interview guide in [Appendix D](#).

9.2.4 Safety endpoints

Observation period for safety endpoints:

The observation period of safety data will be divided into 3 segments:

- The pre-treatment period is defined as the time between the date of the informed consent and the first injection of open-label IMP
- The treatment-emergent AE (TEAE) period is defined as the time from the first injection of open-label IMP up to 2 days after the last injection of IMP
- The post-treatment period is defined as the time starting 3 days after last injection of open-label IMP (after the TEAE period)

The baseline value for safety endpoints will be the last available value prior to the first injection of IMP.

9.2.4.1 Adverse events

Adverse events and SAEs, including injection site reactions. Refer to [Section 10.4](#) to [Section 10.6](#) for details.

9.2.4.2 Product technical complaints

Refer to [Section 8.1.2.4](#) for details.

9.2.4.3 Laboratory safety variables

[figure not shown]
For WOCBP, urine pregnancy test will be performed at Week 4, Week 8, Week 16, and Week 24. It can be confirmed with a serum test if needed. No other laboratory safety variables will be measured after baseline.

9.2.4.4 Hypoglycemia

9.2.4.4.1 Definition of hypoglycemia

Hypoglycemia events will be categorized as follows (following the American Diabetes Association [ADA] Workgroup on Hypoglycemia) (18). Classification of hypoglycemia is summarized in [Figure 1](#).

Figure 1 – Classification of hypoglycemia

- **Severe hypoglycemia**

Severe hypoglycemia is an event requiring assistance of another person to actively administer carbohydrate, glucagon, or other resuscitative actions. These episodes may be associated with sufficient neuroglycopenia to induce seizure, unconsciousness or coma. Plasma glucose measurements may not be available during such an event, but neurological recovery attributable to the restoration of plasma glucose to normal is considered sufficient evidence that the event was induced by a low plasma glucose concentration.

The definition of severe hypoglycemia includes all episodes in which neurological impairment was severe enough to prevent self-treatment and which were thus thought to place patients at risk for injury to themselves or others.

Note that “requires assistance” means that the patient could not help himself or herself. Assisting a patient out of kindness, when assistance is not required, should not be considered a “requires assistance” incident.

Severe hypoglycemia will be qualified as an SAE only if it fulfills SAE criteria. All events of seizure, unconsciousness or coma must be reported as SAEs.

- **Documented symptomatic hypoglycemia**

Documented symptomatic hypoglycemia is an event during which typical symptoms of hypoglycemia are accompanied by a measured plasma glucose concentration of ≤ 70 mg/dL (3.9 mmol/L).

Clinical symptoms that are considered to result from a hypoglycemic episode can include (but are not necessarily limited to): increased sweating, nervousness, asthenia, tremor, dizziness, increased appetite, palpitations, headache, sleep disorder, confusion, seizures, unconsciousness, and coma.

Patients will be instructed to measure finger stick plasma glucose levels prior to the administration of carbohydrates whenever symptomatic hypoglycemia is suspected, unless safety considerations necessitate immediate glucose rescue prior to confirmation, and then a glucose measurement should be performed as soon as safe, with appropriate diary documentation. Details on hypoglycemia episodes will be captured in the patient diaries, and patients will contact the sites as soon as possible following severe events to review the details and decide on any necessary measures to be taken.

- **Asymptomatic hypoglycemia**

Asymptomatic hypoglycemia is an event not accompanied by typical symptoms of hypoglycemia but with a measured plasma glucose concentration less than or equal to 70 mg/dL (3.9 mmol/L).

- **Probable symptomatic hypoglycemia**

Probable symptomatic hypoglycemia is an event during which symptoms typical of hypoglycemia are not accompanied by a plasma glucose determination, but was presumably caused by a plasma glucose concentration less than or equal to 70 mg/dL (3.9 mmol/L); symptoms treated with oral carbohydrate without a test of plasma glucose.

- **Relative hypoglycemia**

Relative hypoglycemia recently termed “pseudo-hypoglycemia” (19) is an event during which the person with diabetes reports any of the typical symptoms of hypoglycemia with a measured plasma glucose concentration >70 mg/dL (>3.9 mmol/L) but approaching that level.

- **Nocturnal hypoglycemia**

Nocturnal hypoglycemia is any hypoglycemia of the above categories that occurs:

- Between 00:00 and 05:59, regardless whether patient was awake or work up because of the event
- Sleep status: patient was asleep between bedtime and before getting up in the morning, ie, before the morning determination of fasting pre-breakfast SMPG and patient woke up due to the hypoglycemia

9.2.4.4.2 *Reporting hypoglycemia*

All hypoglycemia episodes will be documented on the dedicated hypoglycemia event page in the e-CRF. The information about the hypoglycemic events including onset date/time, counter-measurements, whether the patient needed assistance from other to treat the hypoglycemic event, etc. will be collected to support hypoglycemia analyses.

Hypoglycemic events and the symptoms accompanying the events will not be reported as an AE. However, symptomatic hypoglycemia events fulfilling the criteria of an SAE will be documented

on SAE complementary forms in the e-CRF in addition to the hypoglycemic event form. All hypoglycemic events resulting in seizure, unconsciousness, or coma will be reported as SAEs.

For more details on the analysis of hypoglycemia, refer to [Section 11.4.3.4](#).

9.3 FUTURE USE OF SAMPLES

Not applicable.

9.4 APPROPRIATENESS OF MEASUREMENTS

The purpose of the pilot study is to evaluate the methodology of a virtual clinical trial conduct in management of diabetes in the patients with T1DM. The primary endpoint (HbA1c) is well accepted by medical society and the health agencies as a stable indication for glycemic control. Secondary endpoints aim at measuring the appropriate utilization of virtual approach via new technologies during the study; therefore, multiple endpoints are chosen to assess the effect of the virtual versus traditional study conduct on a number of the study activities, including diabetes questionnaires, IMP/NIMP compliance, patient retention, protocol deviation, etc.

The usability and appropriateness of the virtual methodology will also be assessed by a battery of PRO questionnaires. The satisfaction questionnaires (WIWI) will reveal the patient experience of the trial participation from patient's perspective; the WPAI-SP questionnaire will assess the impact of trial participation on the patients' daily life and working hours; the OSEP questionnaire will measure the patient burden with trial participation; and the RUQ will evaluate the number of healthcare professional visits and the associated cost.

Patients in both virtual and traditional groups will receive the exactly same insulin regimen using Toujeo as the basal insulin plus rapid-acting insulin analogs to treat their T1DM during the treatment period. With the HbA1c stratification at the randomization, the baseline HbA1c is expected to be similar in the two groups. The 24-week treatment is considered sufficient for the purpose of the study: after switching from insulin glargine 100 U/mL (eg, Lantus or Basaglar) in a stable dose prior to the study entry, steady state is expected to be reached within 2 weeks of treatment start with Toujeo and the optimal dose of Toujeo is expected to be reached within 8 weeks following fasting SMPG-orientated dose titration regimen.

Thus, the operational effect of the study methodology on glycemic control will be well measured by the change in HbA1c from baseline to Week 24, which is a widely accepted standard endpoint for assessing the glycemic control. Other glycemic variables (FPG, SMPG) will also be assessed. In addition to the laboratory variables, diabetes control will be evaluated by 3 well established PRO questionnaires (DTSQ, HFS-II and DDS) to assess the treatment satisfaction, the hypoglycemia fear, and the diabetes related stress.

Safety will be evaluated by standard clinical measurements, including TEAE, SAE, adverse event of special interest (AESI), and AE leading to IMP discontinuation. Specific safety parameters of interest for a glucose lowering injectable peptide such as hypoglycemia and injection site reactions will also be assessed.

10 STUDY PROCEDURES

This is an approximately 28-week outpatient study. Screening procedures will be performed as a virtual visit followed by a Homecare in-person visit. Eligible and consenting patients will be randomized to an approach group at telephone Visit 2-Step 1, which will determine the way the next visits are organized:

- Traditional group: 5 onsite visits and 7 telephone visits
- Virtual group: 11 virtual visits and 1 mixed onsite-virtual visit (Visit 2-Step 2)

Additional, optional virtual or telephone visits (according to the approach group) will be scheduled to monitor and support the progress of insulin titration whenever considered necessary by the investigator. For both groups, unscheduled onsite visits or Homecare physician visits (depending on the patient's location) may be scheduled only for safety assessment if deemed necessary by the investigator (ie, performance of physical examinations is critical to determine a diagnosis or further evaluation procedure for an AE).

All onsite visits should take place in the morning at approximately the same time. On the day before each onsite visit, patients should be reminded to bring the medical devices (glucose meter), diaries and IMP (used, in-use or unused) to sites and to be in the fasted status if required at some visits.

The **fasting condition** is defined as an overnight fast no less than 8 hours that consisted of no food or liquid intake, other than water. IMP and noninsulin antidiabetic medication should be administered after the fasting blood sample is drawn for all laboratory tests.

Note: If the patient is not in fasting conditions at visits which required in fasting conditions, the blood sample is not collected and a new appointment should be given to the patient for the following day if possible, with instruction to be fasted.

For phone-call visits and virtual visits, the patient is called by the investigator or qualified designee at a scheduled time.

A visit window of ± 3 days using the day of Visit 2-Step 2 as reference is acceptable (4 days for Visit 6, Visit 8, and Visit 10).

If one visit date is changed, the next visit should take place according to the original schedule, ie, counting from Day 1 on Visit 2-Step 2.

Diet and lifestyle counseling including training in carbohydrate counting, if chosen to be used for the mealtime insulin titration, will be continued during the study. Dietary and lifestyle counseling should be given by a registered dietician or other medically qualified person (eg, diabetes educator, endocrinologist) and should be consistent with the recommendations of national or local guidelines (with regard to distribution of calories among carbohydrates, proteins, fats and to exercise) for individuals with type 1 diabetes.

Compliance with the diet and lifestyle recommendations will be discussed with the patients throughout the study, and more specifically in case of insufficient glucose control.

For a complete list of procedures scheduled for each study visit please refer to the study flowchart ([Section 1.2](#)). The aim of the following sections is to provide details on how some of the procedures have to be performed.

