- g* EOT assessments will also be performed for any patients who prematurely discontinue the study treatment. Patients should continue the study procedure as planned up to the EOS after IMP discontinuation.
- h* Heart rate and blood pressure (sitting position)
- i* 7-point SMPG profile (before [preinjection after randomization] and 2 hours after breakfast, lunch and dinner, and at bedtime): at least ONE day during the weeks before Visit 2-Step 2 (Week 0), Visit 10 (Week 16), and Visit 12 (Week 24)
5-point SMPG profile (before breakfast, lunch and dinner; 2 hours after a main meal [or as per investigator's instruction] and at bedtime): at least 3 days during the week before each visit
The SMPG before breakfast should be measured in the fasting status, ie, after the patient wakes up, before breakfast, and before injection of any insulin; preferably no food should have been taken overnight. A note should be made in the diary if the SMPG is not tested in fasting status (eg, if food was taken to cope with a hypoglycemic episode)
- j* Only for patients randomized in the traditional group
- k* Blood samples will be sent to and analyzed by Quest® central lab
- l* Hematology: erythrocytes, hemoglobin, hematocrit, leukocytes and platelets. Clinical chemistry: total bilirubin (in case of values above the normal range, differentiation in conjugated and non-conjugated bilirubin), AST, ALT, ALP, plasma glucose, creatinine, estimated creatinine clearance, uric acid, sodium, and potassium
- m* Urine analysis by dipstick: pH, glucose, ketones, leucocytes, blood/hemoglobin, protein
- n* For women of child-bearing potential (WOCBP): serum pregnancy test for screening; urine pregnancy test for subsequent monitoring and it can be confirmed with a serum test if needed. For WOCBP in virtual group, the urine pregnancy test kit will be provided by the study.
- o* For patients randomized to the virtual group, all questionnaires will be performed remotely via the mobile technology at home. For patients randomized in the traditional group, the questionnaires will be completed electronically (via the mobile technology) at the study site (before visiting the study site for baseline assessment on Visit 2 Step 2).
- p* In a subset of patients (approximately 30) in the virtual approach group.

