9.1 PRIMARY ENDPOINT

- Change in HbA1c from baseline to Week 24.

For the eligibility and efficacy assessments of the study, HbA1c is measured by a certified level I “National Glycohemoglobin Standardization Program” (NGSP) central laboratory.

HbA1c is assayed at screening (Visit 1 – Step 2, Week -2); at Visit 10 (Week 16); Visit 12 (Week 24; final primary endpoint assessment visit).

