Additionally, at Visit 10, patients should be fasted and blood will be drawn for measurements of HbA1c and FPG at central laboratory. The patients from the virtual approach group will attend the local Quest laboratory with the study requisition to complete the blood sampling (for patients located in Canada, phlebotomy may be done by the Homecare nurses at the patients' home or other suitable location).

For a complete list of procedures scheduled for each study visit please refer to the study flowchart ([Section 1.2](#)).

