10.1.5 End of Treatment (EOT) visit (Visit 12, Week 24)

The EOT visit will occur onsite for the traditional approach group. Virtual approach group patients will have the corresponding visit as virtual visit.

Before the EOT visit, the patients will be reminded to:

- perform at least one day of 7-point SMPG during the week prior to the visit. The visit will be postponed if the patient has not done or missed data point(s) of the 7-point profile
- be fasted for about 8 hours prior to on-site visit (traditional group) or presentation to the local laboratory for blood draw (virtual group)
- bring the glucose meter and used and all unused IMP to the sites (traditional group) or as instructed by the study sites (virtual group)

The following will be performed at the EOT visit:

- Vital signs including BP and HR, body weight will be assessed and collected on site (traditional group) or via virtual device (virtual group)
- The questionnaires at the EOT will be performed electronically by the patients. The following questionnaires will be administered: DTSQs, DTSQc, DDS, HFS, WIWI, WPAI-SP, OSEP part 1 and 2, and RUQ. Investigators will be asked to complete the OSES part 1 and 2 questionnaire. The PROs should be completed prior to any other procedure to ensure no impact of site-patient interaction on responses. A subset of patients will be interviewed ([Section 9.2.3.2](#)).
- Blood sampling for laboratory tests will be done at study site, local Quest laboratory, or by Homecare nurse (virtual group patients in Canada only)
- The last IMP must be injected no earlier than completion of all the EOT assessment. Patients of the traditional group will return all their used and unused IMP to the site for accountability and destruction at the EOT visit. For patients of the virtual group, Marken driver will retrieve all used and unused IMP at patients' home after the EOT visit and will return them to the site for accountability and destruction.
- IRT call will be made to register the EOT for the patient

For a complete list of procedures scheduled for this study visit please refer to the study flowchart ([Section 1.2](#)).

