2.5.2 Data handling conventions for secondary efficacy variables

Fasting condition

FPG measurement not collecting in fasting condition will not be used in the analyses.

Invalid laboratory data

HbA1c or FPG measurements flagged as invalid by the laboratory will not be used in the analyses.

Handling of missing data in the calculation of SMPG variables

At least 4 measurements from the 7 points profile are required for analyzing the profile by timepoint, the 24-hour mean SMPG and the corresponding variability.

At least 3 measurements from the 5 points profile are required for analyzing the profile by timepoint.

At least 3 fasting (prebreakfast) SMPG values in the last 7 days are required for calculating the mean of the fasting SMPG.

Patient Reported Outcomes and Clinician Reported Outcomes

Was It Worth It (WIWI)

No total score is calculated. Each item will be analysed separately with all available data ie. with no imputation

Work Productivity and Impairment (WPAI) Questionnaire

See [Appendix D](#)

Overall Study Experience-Participation (OSEP) Questionnaire

For OSEP (Part 1), no total score is calculated. Each item will be analysed separately with all available data ie. with no imputation. For participants with data at one timepoint only – for example, Visit 2-Step 2 but not Visit 12 - they will be excluded from the analysis.

For OSEP (Part 2), no total score is calculated. Each item will be analysed separately with all available data ie. with no imputation.

Resource Use Questionnaire (RUQ)

No total score is calculated. For analysis of average on-treatment RUQ score, all available data will be used and no imputation will be completed. For a participant with only 3 post-baseline RUQ completions, the average for each item will be taken of these 3 scores. For a participant with 10 post-baseline RUQ completions, the average for each item will be taken of these 10 scores.

Overall Study Experience-sites (OSES) Questionnaire

For OSES (Part 1), no total score is calculated. For analysis of average on-treatment OSES (Part 1) time score, all available data will be used and no imputation will be completed. For a participant with only 3 post-baseline OSES-Part 1 completions, the average will be taken of these 3 scores. For a participant with 10 post-baseline OSES-Part 1 completions, the average will be taken of these 10 scores.

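### The fasting rule defers, and can lose, a primary-endpoint HbA1c value that the SAP would accept from a non-fasting patient

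*Protocol*

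**What the plan says.** Protocol Section 10 has a note for visits that require fasting. For a patient who has not fasted, "the blood sample is not collected and a new appointment should be given to the patient for the following day if possible", with an instruction to fast before it. The note does not distinguish one test from another.

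Visits 10 and 12 are such visits. For Week 16, Section 10.1.4 states: "at Visit 10, patients should be fasted and blood will be drawn for measurements of HbA1c and FPG at central laboratory". For Week 24, Section 10.1.5 asks both groups to fast for about 8 hours before the draw. The flow chart in Section 1.2 puts HbA1c and FPG on a single line at the same visits. Section 9.1 schedules HbA1c at screening, Week 16 and Week 24 only, and names Week 24 as the primary assessment.

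SAP Section 2.5.2 treats the two tests differently. On fasting it says: "FPG measurement not collecting in fasting condition will not be used in the analyses". The only exclusion there that reaches HbA1c is laboratory invalidity: "HbA1c or FPG measurements flagged as invalid by the laboratory will not be used in the analyses".

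**The concern.** The collection rule is stricter than the analysis rule. Fasting status decides whether an FPG value is usable. Under the SAP it has no bearing on whether an HbA1c value is usable. Because the two share a draw and the Section 10 note covers the whole sample, a condition that matters for a secondary endpoint controls collection of the primary one.

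HbA1c has only two planned post-baseline measurements, and the note applies to both. A missed redraw at Week 24 removes the primary observation. A missed redraw at Week 16 removes the only other post-baseline value the primary model can use for that patient. Either loss would be avoidable, since the patient was present and a usable HbA1c could have been taken.

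**Working it through.** **Step 1. The rules side by side, for a patient who arrives non-fasting at Visit 10 or 12.**

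| | HbA1c | FPG |
|---|---|---|
| Collected that day (Protocol Section 10) | No | No |
| Usable in analysis if collected (SAP 2.5.2) | Yes, unless flagged invalid | No |

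The protocol and SAP agree for FPG and disagree for HbA1c.

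**Step 2. What must happen for a value to be lost.** The patient must attend non-fasting and then not be redrawn in time. The time available is:
- Protocol Section 10 and flow chart: ±4 days at Visit 10, ±3 days at Visit 12.
- SAP Table 3 (Section 2.5.4), extended by Section 2.5.5 to unscheduled central-laboratory HbA1c: Week 16 target day 113, window 85-140; Week 24 target day 169, window 141-196. A redraw can fall 140 − 113 = 27 days, or 196 − 169 = 27 days, after the target day and still be assigned to the visit.

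So the ordinary result is deferral, and loss occurs only when the redraw fails.

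**Step 3. The plan's precision figure.** Inputs from Protocol Section 11.1: 75 per arm, SD 1.1, up to 10% non-evaluable, two-sided 95% interval, stated precision about 0.37.
- Evaluable per arm: 75 × 0.90 = 67.5.
- Half-width for the difference: 1.96 × 1.1 × √(2/67.5) = 0.371.

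The stated 0.37 reproduces for the between-group difference.

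**Step 4. Extra loss on top of the planned 10%.** The documents give no rate, so these are assumed totals.
- 12% in both arms, n = 66: 1.96 × 1.1 × √(2/66) = 0.375.
- 15% in both arms, n = 63.75: 0.382.
- 20% in both arms, n = 60: 0.394.
- 10% in one arm and 20% in the other: 1.96 × 1.1 × √(1/67.5 + 1/60) = 0.383.

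**Step 5. An illustrative count.** Assume 5-15% of patients attend non-fasting and 25-50% of those are never redrawn. Values lost per arm run from 75 × 0.05 × 0.25 = 0.9 to 75 × 0.15 × 0.50 = 5.6. The planned allowance is 75 × 0.10 = 7.5 per arm. If the upper count came entirely on top of that allowance, n = 67.5 − 5.6 = 61.9 and the half-width would be about 0.388. Both rates are assumptions, and the result depends heavily on the second.

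**The case against.** The strongest reply is that the draw is rebooked, not abandoned. The note says a new appointment should be given, and its qualifier most naturally attaches to the next day rather than to the appointment itself. The windows in Step 2 allow a late redraw to count. Section 10.1.5 also holds the last injection until the end-of-treatment assessments are complete, and the primary analysis uses data regardless of treatment discontinuation. A patient with a Week 16 value stays in the repeated-measures model without Week 24. The study is a descriptive pilot, and Step 4 shows little change in precision. All of this stands and limits the size of the point. It does not explain why a usable HbA1c sample should be deferred.

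Three stronger inferences are tempting, and the documents do not support them.
- *That the loss falls on patients with recent hypoglycemia and so undermines the missing-at-random assumption.* Flow chart footnote i does foresee a broken fast ("eg, if food was taken to cope with a hypoglycemic episode"), but it concerns a diary note about self-measured glucose, not attendance for a central-laboratory draw. Nothing suggests that such patients would fail to return.
- *That the rule bites harder in one arm.* US virtual-group patients attend a local laboratory, and the documents do not say how the note is applied there; sampling detail is left to a manual that is not available. Site staff might enforce it more strictly. Against that, the fasting reminder in Section 10.1.3 is worded for the traditional group only, which would mean fewer non-fasting arrivals there. Section 10.1.5 reminds both groups before Week 24. The direction is unknown.
- *That the primary endpoint is withheld altogether.* Only that day's sample is.

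**Conclusion.** The mismatch is clear on the text: Section 10 defers HbA1c for a reason that the SAP applies to FPG alone, and the value is lost if the redraw fails. It is a modest point about avoidable missing primary data, not evidence of bias. Its frequency cannot be taken from the documents. On assumed total losses of 15% to 20% in both arms, the half-width for the difference rises from 0.371 to between 0.382 and 0.394.

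SAP Section 2 records that the trial stopped with 15 randomized patients and would be reported descriptively. For the trial as run, the point is therefore mainly one of reporting, though each missing value is then 1 of 15. Protocol Section 4 presents the study as a pilot ahead of full-scale studies, and the rule should not be carried into those unchanged.

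**What to change.** Amend the note in Protocol Section 10 along these lines: *If the patient is not fasting, the HbA1c sample is still collected at that visit or laboratory attendance; only the FPG sample is deferred to a repeat appointment.* Put the same instruction in the laboratory manual and on the requisitions for site, local-laboratory and Homecare draws, so that one rule governs Visits 10 and 12 in both groups. For the trial as run, report how many HbA1c draws were deferred or missed because the patient had not fasted.

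The change adds no appointment, because the FPG redraw is already provided for. It has real, small costs. A redrawn patient has a second venipuncture, HbA1c and FPG may be dated differently, a US virtual-group patient may need a second requisition, and some patients may be less inclined to return once HbA1c has been taken. That last risk falls on a secondary endpoint, which is a reasonable exchange for securing the primary one.
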